6.1 CRITERIA FOR PATIENT/SUBJECT ELIGIBILITY

The criteria for patient selection will include patients registered at Memorial Hospital with a diagnosis of a primary brain tumor and are suspect for having recurrent disease. Patients will be nonpregnant, have a Karnofsky score of 60 or more, and have no known medical contraindications to MRI and PET scans. The total number of patients expected to enter the protocol is 30. There will be no exclusions based on age, sex or ethnic background; a pregnancy test will be required of women of child-bearing age. Pregnant women will be excluded from this study.

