6.2 PATIENT/SUBJECT INCLUSION CRITERIA

- Registered patient at MSKCC.
- Child-bearing age females must be non-pregnant, non-lactating, and must be using adequate contraception or surgically sterile.
- Karnofsky score of 60 or greater.
- Children that can sit still for 60-90 minutes, without sedation, will be included in this protocol.

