6.3 PATIENT/SUBJECT EXCLUSION CRITERIA

- Patient cannot tolerate lying still for 90 minute sessions in the PET tomograph.

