8.0 PRETREATMENT EVALUATION

Primary pre-treatment evaluation will be based on the evaluation performed as part of the patient's regular medical care at MSKCC. No additional pre-treatment evaluation will be performed.

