- 9.4 A venous catheter will be placed in a superficial hand or arm vein for administration of the radiopharmaceuticals. A second venous catheter will be placed in the opposite hand or arm for "warmed arterialized" venous blood sampling. For the first 20 patients, a blood sample will be obtained just prior to the injection of [11C-methyl]-L-methionine and [18F]-FACBC to measure plasma amino acid concentration at the time of each study. Sequential blood samples will be obtained following [18F]-FACBC infusion and assayed for whole blood and plasma radioactivity, to check for radiolabeled metabolites by HPLC, and to measure plasma amino acid concentration at the time of the study. All catheters will be removed at the end of the day.

- 9.5 After the [18F]-FACBC head scan and ~10-15 min break period, patients will be placed comfortably on the couch and positioned in the GE Advance PET scanner for sequential body imaging. The total time in the scanner for each imaging sequence will be up to 45 minutes. For the first 20 patients, this sequence of scans will be repeated a maximum of three times over a four hour post injection period (approximately two 18-F half lives). The first body scan sequence will commence ~60 min after [18F]-FACBC injection. The second and third sequences will commence at ~2 and ~3 hours post-injection of [18F]-FACBC, respectively, with a break between scans. During the intervals between scans, the patient will come out of the scanner, exercise and will be asked to void completely. To assist correct re-alignment in the scanner for repeat scans, the patient's skin will be "marked" to identify the plane defined by the PET laser during the first scan set. On the second and third scans, the technologist will position each patient field of view so as to align the laser with the skin markings.
- 9.6 Venous blood will be sampled before the methionine and FACBC scans to measure plasma amino acid concentrations. Blood samples (1/2 teaspoon per sample) will be drawn during the FACBC scans to measure the radioactivity level in your blood. Total blood sampled for the two PET studies will be less than 6 tablespoons (less than 90 ml). Whole blood and plasma will be assayed for radioactivity and for radiolabeled metabolites by HPLC.

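### Section 9.6 limits research blood only by a flat total of less than 90 ml, although children may enrol with no minimum age or weight; a body-weight cap for children would be a small safety improvement

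*Combined protocol and SAP*

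**What the plan says.** The limit on total blood is in section 9.6: "Total blood sampled for the two PET studies will be less than 6 tablespoons (less than 90 ml"). The same section describes two kinds of draw. The first is before each scan: "Venous blood will be sampled before the methionine and FACBC scans to measure plasma amino acid concentrations". No volume is given for it. The second is "Blood samples (1/2 teaspoon per sample) will be drawn during the FACBC scans". Section 9.4 adds that "Sequential blood samples will be obtained following [18F]-FACBC infusion and assayed for whole blood and plasma radioactivity", with metabolite and amino-acid assays on the same series. Neither section states how many samples are taken.

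On who may enrol, section 6.1 says "There will be no exclusions based on age, sex or ethnic background" and section 6.2 says "Children that can sit still for 60-90 minutes, without sedation, will be included in this protocol". The single exclusion in section 6.3 is "Patient cannot tolerate lying still for 90 minute sessions in the PET tomograph". No section of the supplied text gives a minimum age or weight, a ml/kg limit, a reduced sampling schedule for children, or an exemption of children from sampling.

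**The concern.** Both the ceiling and the per-sample volume are absolute amounts, so the written rule is the same for a 20 kg child as for a 70 kg adult. A fixed volume takes more per kilogram from the smaller person. The limit therefore protects least the participants who can spare least.

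The draws serve study assays: plasma amino acids, blood and plasma radioactivity, and radiolabelled metabolites. Volume taken for research is something the protocol can control directly, and it deliberately includes children. What is at stake is participant protection. The point does not touch the sample size, the precision statement in section 14.2, or the comparison of the two tracers.

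**Working it through.** **Inputs from the protocol.** Total ceiling: less than 6 tablespoons, given as less than 90 ml (9.6). Sample volume during the FACBC scans: half a teaspoon (9.6). Number of samples and pre-scan volume: not stated.

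**Inputs assumed.** Body weights of 20, 30 and 40 kg for school-age children and 70 kg for an adult. Half a teaspoon is taken as about 2.5 ml.

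**1. The plan's own figure.** 6 tablespoons × 15 ml = 90 ml (88.7 ml at 14.79 ml per tablespoon). The two forms of the ceiling agree.

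**2. Blood per kilogram at the ceiling (upper bounds).** ml/kg = 90 / weight.

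| Weight | ml/kg at 90 ml | Ratio to 70 kg adult |
|---|---|---|
| 20 kg | 90/20 = 4.5 | 70/20 = 3.5 |
| 30 kg | 90/30 = 3.0 | 70/30 = 2.3 |
| 40 kg | 90/40 = 2.25 | 70/40 = 1.75 |
| 70 kg | 90/70 = 1.29, about 1.3 | 1 |

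The ratio holds for any volume V drawn alike from everyone, since (V/20)/(V/70) = 3.5 whatever V is. It is a statement about proportion and says nothing by itself about safety.

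**3. Does the half-teaspoon limit protect small children?** No. It is also flat, and without a stated number of samples it does not bound the total.

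**4. A cap at adult parity.** At 1.3 ml/kg the cap is 1.3 × 20 = 26 ml, 1.3 × 30 = 39 ml and 1.3 × 40 = 52 ml. It stops binding at 90/1.3 = 69.2 kg, above which the 90 ml ceiling applies.

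**5. What the cap leaves for sequential sampling.** Assume two pre-scan draws of 2.5 to 5 ml each, so 5 to 10 ml together. At 20 kg, (26 − 10)/2.5 = 6.4 to (26 − 5)/2.5 = 8.4, or 6 to 8 whole samples. At 30 kg, (39 − 10)/2.5 = 11.6 to (39 − 5)/2.5 = 13.6, or 11 to 13. These counts depend on the assumed pre-scan volumes and on every sequential sample being half a teaspoon. The protocol states the half teaspoon for samples drawn during the FACBC scans and gives no separate volume for the metabolite or post-injection amino-acid assays.

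**The case against.** The case against giving this much weight is good, and most of it stands.

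- **No threshold is crossed.** A reader might infer that 4.5 ml/kg breaches a paediatric limit or is unsafe. The documents contain no such limit, so they cannot support that reading.
- **The ceiling is not the plan.** A reader might also infer that a child would give 90 ml. Section 9.6 says less than 90 ml, and the number of samples is not stated, so the volume actually drawn cannot be worked out.
- **Few small children are likely.** In the first 20 patients a child would need two venous catheters, a 45-minute methionine scan, a 45-minute FACBC head scan and up to three body-scan sequences of up to 45 minutes each, without sedation. Together with 6.2 and 6.3 this makes toddlers improbable and a 20 kg participant an extreme case. It is still not an age or weight floor.
- **The two-study total describes the first 20 patients.** The last 10 have FACBC only with one body scan (9.3), so the ceiling figures do not describe them directly.
- **There is oversight.** A paediatrics investigator is listed, the FACBC studies run under RDRC guidelines, and the consent form needs IRB approval. Section 13.2 allows removal in the patient's best interest. Staff may well draw less from a child, and the consent form may say so. However, 13.2 sets no volume, and nothing in the supplied text requires a smaller draw.

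What survives is narrow: the one written limit on total volume takes no account of body size in a study that admits children.

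**Conclusion.** The point holds as a minor safety improvement. In the supplied text, research blood is capped only by a flat total, with no age or weight floor and no scaling to body size. The rule as written permits up to 4.5 ml/kg at 20 kg, 3.0 at 30 kg and 2.25 at 40 kg, against 1.3 ml/kg in a 70 kg adult.

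This rests on the assumed weights, on reading the ceiling as an upper bound, and on the absence of a paediatric limit from the pages available. If the consent form already carries one, the change is simply to bring 9.6 into line with it. The documents do not show that any child would be harmed, that any standard is exceeded, or that small children will in fact enrol.

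**What to change.** Add a sentence to section 9.6, matched in the consent form. For children, total research blood over the study, including the pre-scan amino-acid draws, will not exceed the lower of 90 ml and 1.3 ml/kg, unless the paediatric investigator and the IRB approve another value. The cap is to be met by dropping sequential time points. The default is adult parity at the existing ceiling and is not offered as a safety threshold; stating it means the rule works even if no other value is agreed. While editing, word the ceiling so that it also plainly covers the last 10 patients, who have one PET study.

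The cost is small. Body weight is already needed for the SUV (10.4), so no new measurement is required. The scientific cost is a sparser plasma, metabolite and blood-dose curve (10.5, 10.6) in any small child enrolled. The paediatric investigator should therefore choose in advance which time points to keep. Adults are unaffected.

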10.0 EVALUATION DURING TREATMENT/INTERVENTION

- 10.1 Reconstructed images will be obtained from the PET data; corrections will be made for randoms, scatter, dead-time, detector inhomogeneity and attenuation. Image data will be calibrated to nCi/cc and decay corrected to the time of injection. Comparisons will be made with the most recent MRI study obtained as part of the patient's standard radiographic assessment. The PET and MRI scans will be digitally co-registered using established methods at MSKCC to facilitate this comparison.
- 10.2 The registered image sets will be displayed simultaneously, facilitating the identification of the correspondence between the lesion(s) in each modality. Volumes of interest created on one modality will be applied to the other modalities, thus enabling direct quantitative comparisons.
- 10.3 Two levels of image analysis will be performed. One level will involve two Nuclear Medicine physicians (or one Nuclear Medicine physician and one Neurologist) who will independently view the full set of registered images. The analysis will involve assessment for the presence or absence of disease using a five point visual scoring system. These assessments will be blinded to the clinical and pathologic results pertaining to the patient, although all imaging studies (including MRI) will be available

(which is standard clinical practice). We chose a five point scale rating disease from 0-4 in terms of probability for the presence of disease (0=no evidence of tumor, 1=probably no evidence of tumor, 2=equivocal for the presence of tumor, 3=probably tumor present, 4=definitely tumor present).

- 10.4 The second level of analysis will be quantitative. Volumes of interest (VOI) will be drawn on the lesions that are positive on the 3-[18F]-FACBC scan; VOI's on remote normal white and gray-matter regions of the brain will also be drawn. The mean of the voxel values within each VOI will be determined for each of the dynamic frames of the 3-[18F]-FACBC study. Profiles will be generated in units of: 1) standard uptake value [$SUV = (\% \text{ dose/g}) * \text{body weight}$] versus time, and 2) the brain tumor-to-gray or white matter ratio versus time. These curves will be evaluated to determine a single, near "optimal" tumor imaging time, for each of the patients. The criteria used in making this assessment will be target to background contrast, robustness (i.e. time insensitivity) and image noise level. The SUV and ratio values at this "optimal" time point will then be compared to similar SUV and lesion to background values determined for the corresponding location within the [11C]-methionine scan..
- 10.5 Radiolabeled metabolites of 3-[18F]-FACBC, if any, in plasma and urine will be assayed by HPLC and % parent compound vs. time profiles will be constructed for plasma and urine, and compared to the tissue radioactivity concentration vs. time profiles calculated above and used for calculating the kinetic parameters.
- 10.6 The absorbed tissue radioactivity dose estimates for 3-[18F]-FACBC will be calculated in the standard manner. Attenuation corrected PET images provide information for the tumor and organ activities directly in units of activity per cubic centimeter. Regions of interest will be drawn within identified normal organs e.g. brain, lung, liver, bladder etc. This data will be plotted versus time post injection and used for determining organ residence times. These organ residence times will be entered into MIRDOSE for determination of the organ dosimetry. MIRDOSE is a personal computer software package for internal dose assessment from tracers used in nuclear medicine [13]. This program calculates the radiation dose to each organ from the activity residing within that organ, as well as the contribution of the penetrating photon emissions from other body organs accumulating significant levels of radioactivity, according to the methodology laid out by the Medical Internal Radiation Dose (MIRD) Committee [14] (MIRD PRIMER 1988).

The plasma and urine radioactivity concentration data (nCi/cc) will be plotted vs. time after injection. The integral of activity-time curve will be calculated from zero to infinity and multiplied by the equilibrium dose constant for 18F to obtain the absorbed dose to blood. The dose to the bladder wall will be determined using the dynamic bladder model of Cloutier et al. [15], as implemented in MIRDOSE using measured clearance data from urine samples.

The dose estimates described above incorporate estimates of the biological clearance of the tracer. Companion calculations will also be performed using the assumption of no biological clearance, i.e. only physical decay from the organ maximum. This is a

conservative “worst case” scenario and does not depend on the accuracy of the organ clearance fits.

- 10.7 Look for potential correlations between the MR and PET scan results obtained from those patients enrolled to 03-028 and the patients’ past medical treatment, as well as the patients’ subsequent medical treatment, progression of the tumor and survival.

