2.0 OBJECTIVES AND SCIENTIFIC AIMS

- 2.1 Demonstrate in a pilot study (n=30) that [18F]-FACBC has equal or better brain tumor imaging characteristics compared to [11C]-methionine.

- 2.2 Determine the biodistribution and clearance of 3-[18F]-FACBC in different tissues/organs of the body using PET, and calculate body and critical organ radioactivity exposure (dosimetry).
- 2.3 The results of this study will be used to support the submission of an investigational new drug (IND) application to the Food and Drug Agency (FDA).
- 2.4 Look for potential correlations between subsequent MR and PET scan results obtained from those patients enrolled to 03-028 and the patients' subsequent medical treatment, progression of the tumor and survival.

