3.0 BACKGROUND AND RATIONALE

- 3.1 A frequent question that neurooncologists and neurosurgeons must address in the management of post-treatment primary brain tumors, is whether a new or expanding brain lesion observed on CT or MR imaging represents recurrent tumor, treatment effects or tissue necrosis [1-6]. This is of particular concern in the management of patients with previously treated low-grade or anaplastic gliomas. Frequently, a patient may have little or no change in clinical neurological status on follow-up clinical visits, but changes in the pattern of contrast enhancement or an expansion of T2, FLAIR or diffusion abnormalities are observed on routine MRI. The question of recurrent disease vs. treatment effect is frequently raised by clinicians in this setting. This question often leads to further studies or a surgical procedure (e.g., needle or open biopsy) to resolve this issue or to confirm the diagnosis of recurrent tumor. The number of needle biopsy specimens is usually limited in surgical practice (due to the risk of hemorrhage) and it is not uncommon for the pathology of the biopsy sample(s) to be read as nonspecific "gliosis" or "inconclusive".
- 3.2 The "functional" imaging capabilities of PET can provide important additional information that will facilitate making patient management decisions. [18F]-fluoro-2-deoxyglucose ([18F]FDG) PET imaging has been used to distinguish recurrent tumor from treatment effects and tissue necrosis for almost two decades. More recently, the advantages of [methyl-11C]-methionine ([11C]MET) PET imaging of brain tumors have been documented in Europe and Japan [7-10]. Functional information, such as glucose utilization and amino acid transport, can be obtained from PET imaging, and these functional/metabolic/transport images are now routinely compared to the abnormal CT or MR images. This comparison is particularly robust following digital registration of the PET and MR/CT images (see below), and provides very useful information for making timely patient management and treatment decisions.

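### The 0-4 tumour scores in section 10.3 are not specified per tracer or compared with a final diagnosis, so they cannot show how FACBC compares with methionine at identifying tumour

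*Combined protocol and SAP*

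**What the plan says.** - **Clinical question.** Section 3.1 asks whether a new or growing lesion "represents recurrent tumor, treatment effects or tissue necrosis". Section 3.4 suggests that a negative functional PET scan could spare some patients surgery.
- **Objective.** Section 2.1 sets out to show that FACBC images brain tumours at least as well as methionine. Only the first 20 of the 30 patients receive both tracers (4.1).
- **Visual analysis.** Section 10.3 plans an "assessment for the presence or absence of disease using a five point visual scoring system", running from 0 (no evidence of tumour) to 4 (definitely tumour). Two readers "independently view the full set of registered images". "These assessments will be blinded to the clinical and pathologic results pertaining to the patient", "although all imaging studies (including MRI) will be available".
- **Quantitative analysis.** Section 10.4 draws volumes of interest on lesions that are positive on the FACBC scan. It then compares SUV and lesion-to-background ratio with the values at the same location on the methionine scan.
- **Outcome.** Section 2.4 looks for correlations of MR and PET results with "subsequent medical treatment, progression of the tumor and survival". Sections 4.6 and 10.7 repeat this and add past treatment.
- **Statistics.** Section 14.0 covers descriptive summaries and the precision of organ values. It does not mention the scores.

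**The concern.** A tumour-probability score is informative about a tracer only if it can be attributed to that tracer and set against what the lesion turned out to be. The plan provides for neither. It names no reference diagnosis, no cut-off for a positive read, no rule for combining the two readers, and no accuracy or agreement analysis.

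The visual analysis is one of only two levels of image analysis. If it cannot speak to tumour identification, the comparison of tracers rests on the uptake measures in 10.4. Those measures treat higher FACBC uptake as better imaging whether the lesion is tumour or treatment effect, which is the distinction that section 3.1 says clinicians need. Section 2.3 intends the results to support an IND application.

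**Working it through.** **1. Is there a figure in the plan to reproduce?** Not for the scores. The only precision statement (14.2) concerns organ values. With a CoV of 24.4%, s = √ln(1 + 0.244²) = 0.2405, and the half-width is exp(1.96·s/√n) − 1. This gives 16.1% at n = 10 and 11.1% at n = 20, matching the stated 16% and 11%. It has no bearing on the visual analysis.

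**2. Can a score be attributed to one tracer?** Section 10.3 has the readers look at the whole registered set with every imaging study available. It does not say whether they record one score or one per tracer. One score would belong to the set as a whole. Two scores would each be given with the other tracer in view. Neither isolates FACBC or methionine.

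**3. Is the score compared with a diagnosis?** Section 10.3 keeps readers blind to pathology and clinical results but states no later comparison with them. Sections 2.4, 4.6 and 10.7 mention progression and survival, but not the scores, pathology, a method, a time point or a definition of progression.

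**4. What does 10.4 do with non-tumour lesions?** Let p be the tumour share among FACBC-positive lesions. Let D_T and D_N be the mean FACBC-minus-methionine differences in ratio among the tumour and non-tumour lesions. The quantity compared is

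p·D_T + (1 − p)·D_N.

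A positive D_N (FACBC taken up more than methionine in treatment effect) raises this figure, although for the clinical question it is a fault. If D_N is zero or negative, FACBC gains nothing from these lesions. FACBC-negative lesions, including correct negatives, do not enter.

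**5. How many patients could be affected?** The documents give no non-tumour share. Assume 20-40%, with one lesion per patient:

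- 20 × 0.20 = 4 and 20 × 0.40 = 8 non-tumour lesions among the paired patients.
- Only FACBC-positive ones enter 10.4. If 25% of them were positive (assumption), the count would be 4 × 0.25 = 1 to 8 × 0.25 = 2.

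So 4 to 8 is a ceiling.

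**6. What would a comparison with diagnosis deliver?** Assume observed sensitivity near 90%, observed specificity near 80%, and every lesion classified. The exact (Clopper-Pearson) 95% limits are the 0.025 quantile of Beta(x, n − x + 1) and the 0.975 quantile of Beta(x + 1, n − x).

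| Non-tumour share (of 20) | Sensitivity | Specificity |
|---|---|---|
| 20% | 14/16 (0.62-0.98) | 3/4 (0.19-0.99) |
| 40% | 11/12 (0.62-1.00) | 6/8 (0.35-0.97) |

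These intervals can describe each tracer but cannot separate the two.

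**The case against.** The strongest reply is that objective 2.1 concerns imaging characteristics in a pilot, not diagnostic accuracy. The hypotheses name lower background activity and absence of metabolites, and tumour versus treatment effect is background motivation. That is a fair reading of the objective, and it is why this point does not invalidate the study. It does not explain why the plan collects a tumour-probability score, blinded to pathology, and then gives it no analysis.

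A second reply is that outcome is already linked to the scans: 2.4, 4.6 and 10.7 plan correlations with progression and survival, and the scores can be read as PET results. This stands in part. It would be wrong to infer that the plan has no link to outcome at all. The link is undefined, however, and does not tell the analyst to tabulate scores by diagnosis.

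A third reply is that the numbers are too small to be useful and the reference standard is weak. Section 3.1 itself says that "it is not uncommon for the pathology of the biopsy sample(s) to be read as nonspecific" or inconclusive, and treatment given after the scan can delay progression, so a treated recurrence could be misclassified as non-tumour. All of this stands. It limits what may be claimed and shapes the classification rule; it does not justify leaving the scores unanalysed.

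**Conclusion.** The point holds in this form: as specified, the visual scores cannot show whether FACBC is equal to or better than methionine at identifying tumour, and the uptake comparison in 10.4 takes no account of final diagnosis. The effect on 10.4 is bounded by 4 to 8 of the 20 paired patients under an assumed 20-40% non-tumour share. It also requires that the lesion be FACBC-positive and that FACBC uptake exceed methionine uptake there.

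Three stronger readings are tempting, and the documents do not support them:

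- **That the scores themselves favour FACBC.** They are not tied to a tracer, so they favour neither. Any tilt comes from the lesion selection and uptake measures in 10.4.
- **That pathology and outcome are already in hand.** Blinding readers to pathology and clinical findings would be consistent with some pathology existing, but eligibility (6.1 to 6.3) requires no biopsy, and progression and survival accrue after the scan.
- **That all 4 to 8 patients would count as successes for FACBC.** That would need every non-tumour lesion to show high FACBC uptake, which nothing in the documents indicates.

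This is a worthwhile, inexpensive improvement to the analysis plan.

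**What to change.** - **Scoring (10.3).** Have the same two readers record a separate 0-4 score for each tracer viewed with MRI, with the two tracer reads separated in time or their order varied to limit carry-over.
- **Lesion classification.** Use pathology where it was obtained in clinical care. Otherwise use follow-up MR and progression over a prespecified window, with a definition of progression and a rule for intervening treatment. Allow an unclassified category and report its size.
- **Reporting (14.0).** For the paired patients, tabulate each tracer's scores by final diagnosis, paired by patient, with counts and exact confidence intervals (for example at a score of 3 or more). Report the 10.4 SUV and ratio comparison separately for tumour and non-tumour lesions. Label all of it descriptive.

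**Cost.** Plan wording, a second score per reader, some scheduling of reads, and the work of classifying lesions. No added readers, scans or biopsies; the follow-up data are those that 2.4 already intends to use. The downsides are an imperfect follow-up standard, some unclassified lesions and the wide intervals shown above, so no claim of superiority or equivalence could rest on the result.

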4.0 STUDY DESIGN

- 4.1 The first set of 20 patients will consent to two PET studies. One study will involve the i.v. administration of a fluorine-18 labeled amino acid analogue, 3-fluoro-aminocyclobutane carboxylic acid (3-[18F]-FACBC) with sequential brain and body PET imaging. The second study will involve i.v. administration of [11C-methyl]-L-methionine for a head imaging study only. An additional set of 10 patients will consent to one type of PET study which will involve administration of [18F]-FACBC only for one brain scan and one body scan.
- 4.2 ~~All~~The first set of 20 patients will first undergo a [11C-methyl]-L-methionine PET study. Whenever possible, approximately two hours later, the same patient will undergo the [18F]-FACBC PET study.
- 4.3 For the first 20 patients, we will attempt to complete both studies on the same day; if this is not possible, the two PET studies will be completed within 1 week of each other.

- 4.4 The 3-[18F]-FACBC and [11C-methyl]-L-methionine PET images will be digitally registered to each other and to corresponding contrast enhanced and FLAIR MR images (from the most recent MR study obtained as part of the patient's standard medical care). Region of interest (ROI) measurements of 3-[18F]-FACBC and [11C-methyl]-L-methionine activity in tumor and remote brain tissue will be obtained from the two data sets and paired comparisons will be performed.
- 4.5 The study will also provide data to determine body and critical organ radioactivity exposure (dosimetry) following 3-[18F]-FACBC administration. These calculations will be based on the biodistribution and clearance of radioactivity from the tissues and organs of the body as determined by sequential PET imaging.
- 4.6 Look for potential correlations between the MR and PET scan results obtained from those patients enrolled to 03-028 and the patients' past medical treatment, as well as the patients' subsequent medical treatment, progression of the tumor and survival. _

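### Section 10.4 measures lesions that are positive on FACBC, so as written a lesion positive on methionine alone drops out of the quantitative tracer comparison

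*Combined protocol and SAP*

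**What the plan says.** Objective 2.1 is to show that "18F]-FACBC has equal or better brain tumor imaging characteristics compared to [11C]-methionine". The quantitative work for it is set out in 10.4, where "Volumes of interest (VOI) will be drawn on the lesions that are positive on the 3-[18F]-FACBC scan", together with VOIs on remote normal white and gray matter. One near-optimal imaging time per patient is then chosen from the FACBC curves: "The criteria used in making this assessment will be target to background contrast, robustness (i.e. time insensitivity) and image noise level". The FACBC SUV and ratio values at this "time point will then be compared to similar SUV and lesion to background values determined for the corresponding location within the [11C]-methionine scan".

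Three other places bear on which lesions are measured:

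- **4.4** plans that "activity in tumor and remote brain tissue will be obtained from the two data sets and paired comparisons will be performed", with no limit to FACBC-positive tumour.
- **10.2** displays the registered images together, "facilitating the identification of the correspondence between the lesion(s) in each modality", and lets a VOI drawn on one modality be transferred to the others.
- **10.3** is a separate visual reading. "The analysis will involve assessment for the presence or absence of disease using a five point visual scoring system", and "all imaging studies (including MRI) will be available" to the readers.

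Section 14 has no rule for FACBC-negative lesions. Only the first 20 patients receive both tracers, so the point concerns them alone.

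**The concern.** The tracer under study decides which lesions count in its own comparison. A lesion seen on FACBC and not on methionine gets a VOI and contributes a ratio that favours FACBC. A lesion seen on methionine and not on FACBC gets no VOI and contributes nothing. To the extent that positivity is judged from the same FACBC uptake that is later compared, the retained lesions have FACBC values selected upward, and the methionine values follow only as far as the two tracers correlate. The FACBC/methionine ratio then leans toward FACBC even if the tracers are equal.

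The comparison serves objective 2.1, and the results are meant to support an IND. A reader could not tell how much of an apparent FACBC advantage came from the choice of lesions. The plan has no test, margin or decision rule, so this is not a claim about false-positive error.

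A secondary, conditional point is the reading time. It is chosen on FACBC partly by target-to-background contrast, which is itself a compared outcome, and no time rule is stated for methionine. This adds to the lean only if methionine is not read by the same procedure.

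**Working it through.** **Reading the text.** 10.4 is the only place that says which lesions receive a VOI, and it names FACBC-positive ones. The transfer provision in 10.2 governs copying a VOI once drawn, not which lesions get one. 4.4 is broader than 10.4 but sets no lesion rule. 10.3 scores the full registered image set and specifies no separate score per tracer, so it need not reveal methionine-only lesions.

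**The plan's own figure.** Section 14.2 gives a CoV of 24.4% and precision of ±16% (n=10) and ±11% (n=20). On the log scale, s = √ln(1+0.244²) = 0.2405. Then exp(1.96×0.2405/√10) − 1 = 16.1% and exp(1.96×0.2405/√20) − 1 = 11.1%. Both reproduce. They concern organ values and do not bear on lesion selection, but they supply a scale.

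**Illustration: inputs.** From 14.2: CoV 24.4% (animal data; s = 0.2405) and 11.9% (lungs, pancreas and spleen; s = 0.1186). Assumed, not in the documents: these CoVs apply to tumour values; lesion log-values are bivariate normal with equal means and SDs; one lesion per patient; correlation ρ = 0.3, 0.5, 0.7, 0.9; FACBC-positive share p = 0.7, 0.8, 0.9. Let z be the normal quantile of 1−p and m = φ(z)/p, giving m = 0.497, 0.350 and 0.195.

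**(a) Hard cut on the compared FACBC value.** Inflation = exp[s(1−ρ)m] − 1. For p = 0.7 and ρ = 0.3: exp(0.2405×0.7×0.497) − 1 = 8.7%. At CoV 24.4%:

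| p | ρ=0.3 | ρ=0.5 | ρ=0.7 | ρ=0.9 |
|---|---|---|---|---|
| 0.7 | 8.7% | 6.2% | 3.7% | 1.2% |
| 0.8 | 6.1% | 4.3% | 2.6% | 0.8% |
| 0.9 | 3.3% | 2.4% | 1.4% | 0.5% |

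At CoV 11.9% the range is 0.2% to 4.2%.

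**(b) Looser call**, correlated 0.7 with the FACBC value and linked to methionine only through it: exp[0.7s(1−ρ)m] − 1 = 0.3% to 6.0% (CoV 24.4%) or 0.2% to 2.9% (CoV 11.9%).

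**(c) Call that mixes the tracers**, with weight w on FACBC and 1−w on methionine: exp[s·m·(2w−1)(1−ρ)/√(w²+(1−w)²+2w(1−w)ρ)] − 1. At CoV 24.4%, w = 0.7 gives 0.2% to 4.1%; w = 0.5 gives 0.0%; w = 0.3 gives −3.9% to −0.2%.

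**(d) Against sampling error.** With n = 20p lesions and the SD of the log ratio taken within the selected lesions, the 95% half-width is exp(t·SD/√n) − 1. For p = 0.7 and ρ = 0.3: SD = 0.258, t = 2.16, n = 14, giving 16.1% against a lean of 8.7%. For p = 0.9 and ρ = 0.9 it is 5.5% against 0.5%. The half-width exceeds the hard-cut lean in all 24 cells (12 at each CoV).

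**(e) Lesions lost.** With a common cut-off, the expected number positive on methionine only is 20 × [p − P(both positive)]: from 0.6 (p = 0.9, ρ = 0.9) to 3.4 (p = 0.7, ρ = 0.3). The same number, positive on FACBC only, stays in.

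**(f) VOIs on lesions positive on either tracer** (4,000,000 simulated lesions per correlation, CoV 24.4%). With equal tracers and a common cut-off, the lean is within 0.01% of zero. With the methionine-positive share 10 points lower or higher (capped at 98%), it is −0.5% to +0.75%. With a true ratio of 0.9 or 1.1 and a common absolute cut-off, it is −0.6% to +1.2%. In all 48 unequal cells it is smaller than under the FACBC-only rule.

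**The case against.** 10.4 does not contain the word *only*. The VOI-transfer provision in 10.2 is symmetric across modalities, and 4.4 sets no positivity limit, so an analyst could draw a methionine-defined VOI without breaching the protocol. This stands as a limit on wording: the omission is what the plan prescribes as written, not something it forbids departing from. It does not remove the point, because no section calls for such a VOI.

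The direction and size depend on an undefined call. Readers have all the imaging in front of them, and a call informed equally by both tracers would produce no lean. This stands too: the one-sided exclusion follows from the text, but the numerical lean is conditional. The CoVs are also borrowed from organ and animal data, so the ranges illustrate the effect and do not bound it.

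In this small pilot the lean lies within sampling error, at most about 55% of the half-width (4.2% against 7.6% at CoV 11.9%). That limits its importance, but sampling error has no preferred direction and this selection does.

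On timing, comparable methionine values may well mean values obtained by the same procedure. Section 9.3 reports that methionine accumulation tends to plateau by 15 to 30 minutes, and contrast is one of three criteria. The timing point is therefore a request for clarification, and no size is claimed for it.

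**Conclusion.** The concern holds. As written, 10.4 leaves lesions positive on methionine alone out of the quantitative comparison and keeps the opposite discordance, and nothing elsewhere in the plan brings them back. 4.4 and 10.4 need to be reconciled.

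The size is not determined by the documents. Under the stated assumptions the lean toward FACBC is at most 8.7%, and it is smaller with higher correlation, a higher positive share, the lower CoV or a looser call. It is nil if the call weights the tracers equally, and it reverses only if the call on the FACBC scan leans more on methionine. Confidence is high in the reading of the text; the numerical lean remains conditional. The point should be fixed because the remedy is cheap and the comparison serves objective 2.1, but it does not invalidate the pilot.

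**What to change.** Amend 10.4 for the 20 paired patients, and align 4.4 with it:

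1. State how positivity is judged, and record it per lesion for each tracer by the same rule.
2. Draw VOIs on every lesion positive on either PET tracer, and apply each VOI to both scans.
3. State that the same time-selection rule applies to both 45-minute dynamic series.
4. Report a paired 2×2 table of lesion positivity by tracer. Call the off-diagonal lesions discordant, not missed, since no reference standard is set.

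The FACBC-positive subset can remain as a secondary description.

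The cost is protocol wording, one recorded call per lesion per tracer, and a few extra VOIs on images already acquired and co-registered. No extra scans or patients are needed. The apparent FACBC advantage may come out smaller. The either-tracer rule removes the one-sided selection but is exactly unbiased only for equal tracers with a common cut-off; otherwise a small lean can remain (−0.6% to +1.2% in the illustration).
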